**Table JAIN.6.1. Safety Population Treatment Group Analyses for 24-Week Interim Analysis, 52-Week Interim Analysis**

Treatment Group	Definition
24-Week Interim Analysis	
PBO	Placebo + TCS at entry to Study JAIN followed up to end of study or treatment change (data censored at treatment change)
BARI 1-mg	BARI 1-mg + TCS at entry to Study JAIN followed up to end of study or dose change (data censored at dose change)
BARI 2-mg	BARI 2-mg + TCS at entry to Study JAIN followed up to dose change (data censored at dose change)
BARI 4-mg	BARI 4-mg + TCS at entry to Study JAIN followed up to dose change (data censored at dose change)
52-Week Interim Analysis	
PBO	Placebo + TCS at entry to Study JAIN
BARI 1-mg	BARI 1-mg + TCS at entry to Study JAIN
BARI 2-mg	BARI 2-mg + TCS at entry to Study JAIN

BARI 4-mg	BARI 4-mg + TCS at entry to Study JAIN
-----------	--

Table JAIN.6.2 describes the treatment groups and the comparisons for each study period and the analysis population by Week 52 DBL.

**Table JAIN.6.2. Treatment Groups and Comparisons for the 52-Week Interim Analysis and Analysis Population**

Study Period	Analysis Population	Treatment Group	Abbreviation	Comparison
52-week Double-Blind Treatment Period (Period 2)	Intent-to-Treat Population	Placebo + TCS	PBO	BARI-4mg vs PBO BARI-2mg vs PBO BARI-1mg vs PBO
		Baricitinib 4-mg + TCS	BARI-4mg	
		Baricitinib 2-mg + TCS	BARI-2mg	
		Baricitinib 1-mg + TCS	BARI-1mg	
		Pooled Baricitinib + TCS (for safety only)	BARI 1-mg/2-mg/4-mg	
		Total	Total	

Abbreviations: BARI = baricitinib; PBO = placebo; TCS = topical corticosteroids.

Table JAIN.6.3 describes the treatment groups and the comparisons for each study period and the analysis population for the Week-104 DBL and Final DBL.

**Table JAIN.6.3. Treatment Groups and Comparisons for the 104-Week Interim and Final DBL Analysis Population**

Study Period	Analysis Population	Treatment Group	Abbreviation	Analyses Category
Long-Term Extension Period (Period 3 and Period 4)	LTE Substudy Population	Bari 4-mg in Period 2, were re-randomized to (Bari 4-mg or Bari 2-mg) in Period 3/Period 4;	Bari 4-mg/4-mg Bari 4-mg/2-mg	Efficacy
	LTE Substudy Population with IGA(0,1) at Week 52	Bari 2-mg in Period 2, were re-randomized to (Bari 2-mg or Bari 1-mg) in Period 3/Period 4.	Bari 2-mg/2-mg Bari 2-mg/1-mg	Efficacy for Subsetting IGA(0,1) at Week 52
	LTE Substudy Relapse Population	Bari 4-mg in Period 2, were re-randomized to (Bari 4-mg or Bari 2-mg) in Period 3/Period 4, retreated with presubstudy of Bari 4-mg when Relapse occurred;  Bari 2-mg in Period 2, were re-randomized to (Bari 2-mg or Bari 1-mg) in Period 3/Period 4, retreated with presubstudy of Bari 2-mg when Relapse occurred.	Bari 4-mg/4-mg/4-mg Bari 4-mg/2-mg/4-mg  Bari 2-mg/2-mg/2-mg Bari 2-mg/1-mg/2-mg	Time to Relapse
	LTE Non-responder Population	Bari 4-mg stays Bari 4-mg in Period 2 & Period 3/Period 4;	Bari 4-mg Bari 2-mg /2-mg Bari 2-mg/4-mg Bari 1-mg/2-mg Bari 1-mg/4-mg PBO/Bari 2-mg PBO/Bari 4-mg	Efficacy

	(Bari 2-mg, Bari 1-mg or Placebo) were re-randomized to (Bari 2-mg or Bari 4-mg) in Period 3.		
Long-Term Extension (LTE) Responders & Partial Responders who did not enter the Substudy	Bari 4-mg, Bari 2-mg Bari 1-mg, Placebo will continue on the same treatment	Bari 4-mg Bari 2-mg Bari 1-mg Placebo	Efficacy
Safety Population	Bari 4-mg, Bari 2-mg Bari 1-mg, Placebo who continuously got treated from baseline and censored in case of dose change.	Bari 4-mg Bari 2-mg Bari 1-mg Placebo All Bari	Safety

Abbreviations: Bari = baricitinib; IGA = Investigator's Global Assessment for AD; LTE = Long-Term Extension; PBO = placebo.

### **6.2.2. General Considerations for Analyses for the 24-Week, 52-Week, , 104-Week Interim Analysis, and Final DBL**

**Period 2** starts at randomization (Visit 2, Week 0) and ends with the visit at Week 52 (Visit 14) or the early discontinuation visit (between Weeks 0 and 52).

**24-week interim analysis** will be done when all the patients complete Week 24 assessment (Visit 10) or discontinue study or treatment before the Week 24 assessment.

**52-week interim analysis** will be done when all the patients complete Week 52 assessment (Visit 14) or the early termination visit (between Weeks 0 and 52).

**Period 3** starts at re-randomization (Visit 14, Week 52) and ends with the visit at Week 104 (Visit 22) or the early discontinuation visit (between Weeks 52 and 104).

**104-week interim analysis** will be conducted when all the patients complete Week 104 assessment (Visit 22) or the early termination visit (between Weeks 0 and 104).

**Period 4** starts at (Visit 22, Week 104) and ends with the visit at Week 200 (Visit 28) or the early termination visit (between Weeks 104 and 200). For the final DBL, efficacy endpoints beyond week 104 will be exploratory in nature and will be analyzed in a descriptive way using observed data.

### 6.2.2.1. Definition of Baseline and Postbaseline Measures

The baseline value for the efficacy and health outcomes is defined as the last non-missing measurement on or prior to the date of first study drug administration (expected at Week 0, Visit 2).

The baseline value for the daily diary assessments (Itch Numeric Rating Scale [NRS], Atopic Dermatitis Sleep Scale (ADSS), Skin Pain NRS, Patient Global Impression of Severity–Atopic Dermatitis [PGI-S-AD]) is defined as the mean assessment of the 7 days prior to the date of first study drug administration. Criteria for derivation of the baseline score requires that there be at least 4 non-missing measurements in the 7 days indicated; otherwise, an expanded window of up to 14 days prior to first study drug administration, if available, may be utilized to obtain the most recent 4 non-missing measurements prior to first study drug administration. If there are at least 4 non-missing assessments are not collected prior to the date of first study drug administration using the aforementioned method, the baseline will be designated as missing.

Baseline for the safety analyses is defined as the last non-missing scheduled (planned) measurement on or prior to the date of first study drug administration for continuous measures, by-visit analyses, and all non-missing measurements on or prior to the date of first study drug administration for all other analyses.

#### *Period 3 and Period 4 (Study Weeks 52 to 200)*

For analysis of endpoints assessed at scheduled visits in Periods 3 and 4, baseline from Week 0 will be used for categorical endpoints, such as EASI75, Itch NRS  $\geq 4$ -point improvement response, etc. Baseline from Week 0 will also be used for EASI-related, continuous endpoints, such as EASI change or percent change from baseline. For the other continuous endpoints such as Itch NRS and Dermatology Life Quality Index (DLQI) change from baseline, the analysis will be done using the Week 52 baseline. The methodology for defining Week 52 as the baseline is the same as the methodology for defining Week 0 of the originating study described above, anchoring on the first study drug administration of Period 3. See [Table JAIN.6.9](#) and [Table JAIN.6.12](#) for a detailed descriptions on endpoint derivation and associated baseline definition.

Baseline daily-diary definition will be same to the Period 2's definition for daily-diary data.

Postbaseline measurements are collected after study drug administration through Week 200 (Visit 28) or early discontinuation visit. Data collected on scheduled visits will generally be used for efficacy and health outcome analyses. If data for a scheduled visit are missing, data from the most proximal unscheduled visits, if available, will be used if it falls within visit windows as follows: a 2-day interval around the scheduled visit day (4-day window) is applied to Visits 3 to 6 (Week 1, 2, 4, 8), a 4-day interval around the scheduled visit day (8-day window) is applied to Visits 7 to 9 (Week 12, 16, 20), a 5-day interval around the scheduled visit day (10-day window) is applied to Visits 10 to 14 (Week 24, 32, 40, 48, 52), a 4-day interval around the scheduled visit day (8-day window) is applied to Visits 15 to 18 (Week 56, 60, 64, 68), a 5-day interval around the scheduled visit day (10-day window) is applied to Visits 19 to 22 (Week 76, 84, 92, 104), and a 7-day interval around the scheduled visit day (14-day window) is applied to

Visits 23 to 28 (Week 120, 136, 152, 168, 184, and 200). If there is more than 1 unscheduled visit within the defined visit window and no scheduled visit is available, the unscheduled visit closest to the scheduled visit date will be used. If only 2 equal distance unscheduled visits are available, the later of the 2 visits will be used.

Postbaseline visits for weekly assessments of daily diary data will be each 7-day visit interval beginning on the day of first study drug administration, creating intervals for Week 1 (Days 1 through 7), Week 2 (Days 8 through 14), Week 3 (Days 15 through 21),..., Week 50 (Day 344 through 350). Each interval will be represented by the mean of that interval. If there are less than 4 non-missing measurements in any weekly interval, the mean for that weekly visit interval will be considered missing. Furthermore, as some analyses require use of the primary censoring rule (Section 6.3), assessments collected on or after the day of rescue will be excluded from the weekly visit interval calculation when implementing this censoring rule. If, after exclusion of those records, there are less than 4 non-missing assessments, the mean of the weekly interval that implements the primary censoring rule will be considered missing.

Week 52 diary window is the 7 days prior to Week 52 (V14) visit date. If Week 52 (V14) visit occurs later than Days 370 (=365+5), the window is from Days 358 through 364. If there is no Week 52 (V14) visit, the Week 52 interval and its associated mean are defined as missing. Week 51 diary window is from Days 351 through 357, but will exclude the dates falling into Week 52 diary window.

Week 53 diary window is from Days 365 through 371, but will exclude the dates falling into Week 52 diary window. Week 54 is from Days 372 through 378; Week 55 is from Days 379 through 385. Week 68 is from Days 470 through 476. If there are less than 4 non-missing measurements in any weekly interval, the mean for that weekly visit interval will be considered missing.

For the Week-104 interim lock, safety analyses will be conducted for adverse events (AE) for Treatment Period 3. The AE baseline period is on/after the first dose date in Period 2 and prior to the date of the first dose date in Period 3 of Study JAIN.

For the Final lock, safety analyses will be conducted for adverse events (AE) on extended safety analysis for which baseline will be Week 0 i.e. on/after the first dose date in Period 2Postbaseline measures for the safety analyses are defined as the non-missing scheduled (planned) measurements after the date of first study drug administration for continuous measures, by-visit analyses, and all non-missing measurements after the date of first study drug administration for all other analyses.

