### **6.3.7. Missingness due to COVID-19**

For missingness that COVID-19 is identified as the cause by the study team, the following imputation methods may be applied.

- For continuous measures, if missing due to COVID-19,
  - When they are analyzed using analysis of covariance (ANCOVA) for a single timepoint, modified last observation carried forward (mLOCF) method may be used (this is the same as missingness due to reasons other than COVID-19).
- For categorical variables, if missing due to COVID-19,

- mLOCF method may be used. This applies to categorical variables that are collected categorically, as well as categorical variables that are derived from measures that are collected as continuous, such as EASI50, EASI75 and EASI90.
  - This is on top of non-responder imputation specified in the sections above.
  - If a visit has missing data due to COVID-19 and the visit prior to this visit has missing data due to other reasons, mLOCF will be applied after the imputation for the prior visit is done.
- In addition, for IGA 0 or 1 and EASI75, multiple imputation (MI) method may be used. Seed = 123456 will be used for MI. Results from MIs will be aggregated to generate the final estimates for statistical inferences. This will be the main imputation method for these primary and key efficacy measures for visits with missing data due to COVID-19.
  - If a visit has missing data due to Covid-19 and the visit prior to this visit has missing data due to other reasons, MI will be applied after the imputation for the prior visit is done.

All measures collected through ePRO diary device should not be impacted by COVID-19. Therefore, no imputation method other than those specified before this section will be used.

For a specific DBL, if COVID-19 is still ongoing at the time of the DBL, the list of visits with missing data due to COVID-19 identified by the study for that lock may not be complete and may be updated in future locks. The imputation for missingness due to COVID-19 for each DBL is based on the list we receive for that specific lock.

For the planned locks to occur on and after July 2021, if the missing data due to COVID-19 does not exceed a prespecified 5% (Lin 2020) for each of the analysis population set, then there would no special imputation method applied.

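### SAP 6.2.2.1 sets the Week 52 diary score to missing for a patient with no Week 52 visit, even if that week's home diary is complete; no primary or key secondary test is affected

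*SAP*

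**What the plan says.** SAP 6.2.2.1 builds weekly diary scores from calendar days counted from first dose. Weeks 1 to 51 and 53 to 68 are fixed seven-day blocks, except that Weeks 51 and 53 give up any day claimed by Week 52. Each block is subject to one completeness rule: "If there are less than 4 non-missing measurements in any weekly interval, the mean for that weekly visit interval will be considered missing".

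Week 52 alone is tied to a clinic visit. The section gives three cases:

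- Visit held on time: "Week 52 diary window is the 7 days prior to Week 52 (V14) visit date".
- Visit held late: "If Week 52 (V14) visit occurs later than Days 370 (=365+5), the window is from Days 358 through 364".
- Visit not held: "If there is no Week 52 (V14) visit, the Week 52 interval and its associated mean are defined as missing".

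The neighbouring weeks do not pick up the days that are then left over: "Week 51 diary window is from Days 351 through 357, but will exclude the dates falling into Week 52 diary window", and "Week 53 diary window is from Days 365 through 371, but will exclude the dates falling into Week 52 diary window".

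Protocol 5.1.2 and 5.1.3 keep the daily diary running through Week 52 and on to Week 68, so entries can exist without a Week 52 visit. SAP 6.3.1 scores a patient whose value is missing at an intermediate visit as a nonresponder at that visit. Tables JAIN.6.4 and JAIN.6.11 apply NRI, under both censoring rules, to 4-point itch improvement at Week 52. On COVID-19, SAP 6.3.7 says: "All measures collected through ePRO diary device should not be impacted by COVID-19". It therefore gives diary measures none of the special imputation that it allows for other endpoints.

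**The concern.** The measurement is made at home, and the clinic visit adds nothing to it. The SAP shows this itself: for a late visit it uses Days 358 to 364, a window that does not depend on the visit date. A patient seen on Day 385 keeps those seven entries; a patient never seen loses the same seven.

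Two kinds of result are exposed.

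- **Categorical.** For 4-point itch improvement at Week 52 (exploratory, SAP 4.3), a patient still on treatment whose diary shows a response is counted as a failure. NRI is justified in 6.3.1 by the assumption that the treatment effect is lost after an intercurrent event. Here the outcome was observed and the effect was not lost. The exploratory Week 52 4-point Skin Pain endpoint would be affected in the same way.
- **Continuous.** For percent change in Itch NRS at Week 52 (other secondary, SAP 4.2.2), and for change in Itch NRS, Skin Pain, ADSS items and PGI-S-AD, real data are discarded and a model or an older value stands in.

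The rule also undermines the premise of 6.3.7. If COVID-19 keeps a patient from Visit 14, the Week 52 diary score is lost through 6.2.2.1, yet 6.3.7 withholds relief because it presumes that diary scores are untouched.

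**Working it through.** **1. Reproduce the SAP's calendar.** Week k covers Days 7(k−1)+1 to 7k. Week 50 is then Days 344–350, Week 51 is 351–357, Week 52 is 358–364, Week 53 is 365–371 and Week 68 is 470–476. The Visit 14 target is 52×7+1 = Day 365, and the 5-day tolerance gives Day 370. All of these agree with 6.2.2.1, so the fallback window "the window is from Days 358 through 364" is simply calendar Week 52.

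**2. Assign the diary days, with a complete diary.**

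| Visit 14 held on | Days used for Week 51 | Week 52 | Week 53 | Days 358–364 left unused |
|---|---|---|---|---|
| Day 365 | 7 | 7 | 7 | 0 |
| Day 371 or Day 385 | 7 | 7 | 7 | 0 |
| not held | 7 | 0 | 7 | 7 |

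The completeness rule asks for 4 entries. The patient without a visit has 7 and is credited with 0.

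**3. Follow the missing score through the analyses.**

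- 4-point itch at Week 52: logistic regression with NRI (Table JAIN.6.11), so the patient is a nonresponder.
- Percent change in Itch NRS at Week 52: MMRM under the secondary censoring rule, with ANCOVA on mLOCF as sensitivity (same table). The patient's other weekly scores stay in the model, and mLOCF carries the last one forward.
- Primary and key secondary tests (SAP 4.1, 4.2.1 and 6.4): all lie at Weeks 1 to 24, so none uses the Week 52 diary score.

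**4. Size of the NRI effect.** Let p be the true response rate and m the share of an arm with a usable diary but no Visit 14. If m is unrelated to response, the reported rate is p(1−m). The documents give neither m nor an itch response rate, so everything below is illustrative.

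With p = 40% and 20% and m = 5%: 0.40×0.95 = 38% and 0.20×0.95 = 19%. The difference falls from 20 to 19 points.

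With 45% and 20%, borrowed from the sample-size section (a 25-point difference over 20% placebo, stated there for EASI75 at Week 16):

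| m, equal in both arms | Active | Placebo | Difference (points) |
|---|---|---|---|
| 0 | 45.00% | 20.0% | 25.00 |
| 1% | 44.55% | 19.8% | 24.75 |
| 2% | 44.10% | 19.6% | 24.50 |
| 5% | 42.75% | 19.0% | 23.75 |
| 10% | 40.50% | 18.0% | 22.50 |

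At m = 5%, 100×0.45×0.05 = 2.25 responders per 100 active patients analysed, and 100×0.20×0.05 = 1.00 per 100 placebo patients, are recorded as failures.

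**5. Unequal shares.** With m = 8% on active and 2% on placebo: 0.45×0.92 − 0.20×0.98 = 0.414 − 0.196 = 21.8 points. With the shares reversed: 0.45×0.98 − 0.20×0.92 = 0.441 − 0.184 = 25.7 points, above the true 25.

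**The case against.** The strongest reply is that hardly anyone is affected. Visit 14 is the re-randomization and dispensing visit, and SAP 6.2.2 closes the 52-week analysis when every patient has had Visit 14 or an early termination visit. A patient without Visit 14 will usually have left early, and someone who permanently stopped drug before Week 52 is a nonresponder under either censoring rule. Near misses are covered: a late visit gets Days 358 to 364, and SAP 6.2 maps an early termination visit inside the window to the scheduled visit. An unscheduled visit inside the window may supply scheduled-visit data, although 6.2.2.1 does not say whether its date anchors the diary window. This stands. The group left is patients on drug, with a kept diary, no Visit 14 and no early termination visit in the window.

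It is also fair that continuous diary endpoints are not left without recourse, since MMRM and mLOCF use the patient's other scores. That stands too: under missing at random, MMRM loses information but need not be biased.

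Four stronger readings are tempting, and the documents do not support them.

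- A reader might infer that a secondary endpoint suffers nonresponder scoring. The secondary Week 52 itch endpoint is percent change, which is not analysed with NRI; the endpoint that is scored this way is exploratory.
- A reader might infer that the treatment difference must shrink. That needs similar missed-visit rates across arms, unrelated to response; step 5 shows it can grow.
- A reader might take the 5% in 6.3.7 as an expected missed-visit rate. It is the level of COVID-19 missing data up to which no special imputation is applied, for locks from July 2021.
- A reader might call 6.2.2.1 and 6.3.7 contradictory instructions. They are not; 6.3.7 rests on a premise that 6.2.2.1 makes untrue at Week 52.

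**Conclusion.** The point holds, with limited reach. The rule discards a diary score that was collected and that the SAP would accept had the visit been late, and the SAP gives no reason for treating an absent visit differently. In the exploratory Week 52 4-point itch analysis it produces a wrong classification for any affected responder. In the continuous Week 52 diary analyses it costs information. The primary and key secondary conclusions are untouched.

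The size is unknown because the number of affected patients is not in the documents; it is probably small. Over an assumed equal share of 1% to 10%, a 25-point difference would be reported as 24.75 to 22.5 points. With unequal shares of 2% and 8% it would be 21.8 or 25.7. These figures rest on borrowed response rates and on missed visits being unrelated to response within each arm.

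**What to change.** In SAP 6.2.2.1, replace the sentence on an absent Week 52 visit with one that extends the existing fallback:

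> Where Visit 14 did not take place, or took place after Day 370, the Week 52 diary interval is Days 358 to 364, provided at least 4 entries are present and after the applicable censoring rule.

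The section should also state whether an unscheduled visit inside the Visit 14 window anchors the diary interval. In 6.3.7, the premise about diary measures becomes tenable at Week 52 once a missed visit no longer removes the score.

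The cost is one sentence and a small program change on data already collected, and the censoring rules still apply. Timing is the real constraint. According to the SAP's revision history, Version 3 covered the 52-week analysis, while Version 5 concerns the final lock and follows the Week 104 lock. If the Week 52 analysis is already locked, keep the planned result and report the corrected window as a labelled supplementary analysis, with the number of affected patients in each arm. That count alone would show whether the rule mattered.

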5.1.2. Period 2: Double-Blind Placebo-Controlled Treatment

At Visit 2 (Week 0, baseline), study eligibility for each patient will be reviewed, based on all inclusion and exclusion criteria (Section 6), and laboratory test results. Patients who meet all criteria will proceed to randomization and begin the 52-week double-blind, placebo-controlled treatment period.

At Visit 2, laboratory samples will be collected and all assessments should be completed before the patient takes the first dose of investigational product. The first dose of investigational product should be administered on-site.

Patients will be randomized at a 1:1:2:1 ratio to 1 of 4 treatment groups (placebo QD, baricitinib 1-mg QD, baricitinib 2-mg QD, or baricitinib 4-mg QD). Patients will also apply background TCS therapy (e.g., triamcinolone 0.1% cream and/or hydrocortisone 2.5% ointment) on active lesions, as described in Section 7.7.2 (Use of Topical Corticosteroids). Use of TCIs and/or crisaborole (where approved) will be permitted as background therapy on areas where application of TCS is considered inappropriate by investigator (e.g., face, neck, skin folds, genital areas; see Section 7.7.1 [Permitted Medications and Procedures]). High- or ultra-high potency TCS (Class I to III; see Appendix 7) and all systemic therapies used for treating AD will not be allowed, unless used as directed as part of rescue therapy (see guidelines in Section 7.7.5 [Rescue Therapy]) and only at the discretion of the investigator. Rescue to baricitinib will not occur during treatment Period 2.

Assessments of disease severity will be performed by the investigator at all study visits including unscheduled and early termination visits (ETVs). On study visit days, patients are requested not to apply emollients nor TCS until after the assessments are completed. Daily diary collection will continue through all 52 weeks of treatment in Period 2 of JAIN.

The primary efficacy endpoint will be at Week 16 (Visit 8). All patients who permanently discontinue investigational product prior to the primary endpoint, including patients rescued with other systemic medications, should remain in the study to complete the schedule of study visits per protocol up to Week 16 (primary endpoint), when they will complete an ETV. If the patient refuses to continue up to Week 16 and wishes to withdraw consent, an ETV should be completed as soon as logistically possible.

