5.1.3. Period 3: Double-Blind, Long-Term Extension

Patients who complete the study through Week 52 will progress into the double-blind long-term extension phase through Week 104 (Visit 22). Daily diary collection will continue through Week 68 (Visit 18) of Period 3.

Concomitant use of background TCS therapy will continue during this treatment period as described in Section 7.7.2.

5.1.3.1. Randomized Downtitration Substudy at Week 52

At Week 52, all patients will be evaluated for substudy eligibility. To be eligible, a patient must meet all of the following criteria:

- have an IGA 0, 1 (Responder) or 2 (Partial responder) at Week 52
- have not used high- or ultra-high potency TCS in the last 14 days (potency classification in [Appendix 7](#))
- do not currently have study drug interrupted
- have been assigned to baricitinib 2-mg or 4-mg at baseline (assessed by interactive web-response system [IWRS])

Treatment

Treatment in the substudy is illustrated in [Figure JAIN.1](#). Patients eligible for the substudy will be rerandomized at a 1:1 ratio at Week 52 based on the baricitinib treatment group assigned at baseline:

- 4-mg QD rerandomized to baricitinib 4-mg QD, or baricitinib 2-mg QD
- 2-mg QD rerandomized to baricitinib 2-mg QD, or baricitinib 1-mg QD

Note: Intensification of emollients and TCS may be continued or initiated to control worsening and unacceptable symptoms of AD any time during this treatment period. For management of TCS, follow the guidelines in [Section 7.7.2](#).

Retreatment

During the substudy, if worsening of AD symptoms occurs such that IGA increases to ≥ 3 , the patient will be automatically retreated with their presubstudy baricitinib dose. When the IGA is ≥ 3 , the investigator should reinstate background TCS therapy (e.g., triamcinolone 0.1% cream and/or hydrocortisone 2.5% ointment), provided the patients are not currently using TCS, and may prescribe high- or ultra-high-potency TCS following the guidelines for use of Rescue Therapies ([Section 7.7.5](#) [Rescue Therapy]). An unscheduled visit may be needed to assess worsening of symptoms and to perform clinical safety and efficacy assessments immediately before retreatment.

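### The fixed Week 68 diary window can outrun the diary itself: a patient who attends Visit 18 two to four days early has only 4 to 6 possible entries against a minimum of 4 (minor, cheap to fix)

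*SAP*

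**What the plan says.** SAP 6.2.2.1, under the Period 3 and Period 4 subheading, builds diary weeks as "each 7-day visit interval beginning on the day of first study drug administration". Week 68 follows that pattern: "Week 68 is from Days 470 through 476". A completeness rule applies: "If there are less than 4 non-missing measurements in any weekly interval, the mean for that weekly visit interval will be considered missing".

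The same section handles Week 52 differently: "Week 52 diary window is the 7 days prior to Week 52 (V14) visit date", with a calendar fallback for late visits and the overlapping days removed from Weeks 51 and 53.

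On visit timing, "a 4-day interval around the scheduled visit day (8-day window) is applied to Visits 15 to 18", which includes Week 68. The Schedule of Activities in the protocol gives the same tolerance. It shows the diary last dispensed at Visit 17 and last returned, as a scheduled visit, at Visit 18. Protocol 5.1.3 agrees: "Daily diary collection will continue through Week 68 (Visit 18) of Period 3". Footnote h of the Schedule asks patients to complete Itch NRS, Skin Pain NRS, ADSS and PGI-S-AD before the clinical assessments on visit days.

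Table JAIN.6.12 reports these outcomes for Weeks 52 to 68, as observed and with mLOCF.

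**The concern.** Days 470-476 are the seven days before an on-time Visit 18. If the visit is early, the tail of the window lies after the diary has been handed back, and those days can never be filled. Entries the patient made on Days 466-469 exist but do not count towards Week 68.

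Week 68 is 16 weeks after re-randomisation. SAP 4.3 names it for all four diary outcomes, and no diary data follow it. When the score is missing, the observed summary loses a patient who may have met both the visit tolerance and a reasonable standard of diary completion. The mLOCF summary substitutes an earlier week, normally Week 67, where the dose-change and censoring limits in SAP 6.3.3 allow.

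**Working it through.** **Reproducing the SAP's day numbers.** Week w covers Days 7(w−1)+1 to 7w. For w = 68 this gives 7×67+1 = 470 to 7×68 = 476, as stated. Weeks 50, 53, 54 and 55 also match.

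**Range of Visit 18.** The SAP puts the scheduled Week 52 visit at Day 365 = 7×52+1. By the same convention Week 68 is Day 7×68+1 = 477, so ±4 days gives Days 473-481. This takes Day 1 as Visit 2, which the protocol supports (5.1.2): "The first dose of investigational product should be administered on-site".

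**Possible entries in Days 470-476.** Visit day v minus 469 with a visit-day entry, or v minus 470 without one, capped at 7. The minimum is 4.

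| Visit 18 on | With visit-day entry | Without | Misses tolerated (with entry) |
|---|---|---|---|
| Day 473 | 4 | 3 | 0 |
| Day 474 | 5 | 4 | 1 |
| Day 475 | 6 | 5 | 2 |
| Day 476 | 7 | 6 | 3 |
| Day 477 or later | 7 | 7 | 3 |

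**Chance of a missing score.** Assume each day is completed independently with probability c. Two readings of the visit day are shown:

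- A: the visit day is completed with probability c like any other, so P(missing) = P(Bin(n, c) ≤ 3).
- B: the visit-day entry is always made, as footnote h asks, so P(missing) = P(Bin(n−1, c) ≤ 2).

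| Visit 18 on | A, c = 90% | A, c = 80% | B, c = 90% | B, c = 80% |
|---|---|---|---|---|
| Day 473 (n = 4) | 34.4% | 59.0% | 27.1% | 48.8% |
| Day 474 (n = 5) | 8.1% | 26.3% | 5.2% | 18.1% |
| Day 475 (n = 6) | 1.6% | 9.9% | 0.9% | 5.8% |
| Full 7 days (reference) | 0.3% | 3.3% | 0.3% | 3.3% |

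Example: Day 473 under A at 90% is 1 − 0.9⁴ = 0.344; under B it is 1 − 0.9³ = 0.271.

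**Averaging over visit days**, as excess over the 7-day reference:

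- Even spread over Days 473-481, reading A. At 90%: (0.341 + 0.079 + 0.013)/9 = 4.8%. At 80%: (0.557 + 0.229 + 0.066)/9 = 9.5%. Reading B gives 3.6% and 6.8%.
- Visits clustered on schedule (rounded normal, SD 2 days, limited to Days 473-481; weights 0.0285, 0.0672 and 0.1240 on Days 473-475), reading A. At 90%: 0.0285×0.341 + 0.0672×0.079 + 0.1240×0.013 = 1.7%. At 80%: 3.9%. Reading B gives 1.1% and 2.3%.

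At 95% completion, reading A gives 2.3% (even) and 0.7% (clustered). If nobody makes a visit-day entry, the excess at 80-90% completion is 16-20% (even) and 6-11% (clustered), but that departs from footnote h.

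**The case against.** A reader might infer that early attenders are simply set to missing. The documents do not support that. With the visit-day entry that footnote h asks for, every permitted visit day leaves at least 4 possible entries. A missing score is forced only at Day 473 with no visit-day entry.

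A reader might also infer that the SAP already solved this problem at Week 52 and overlooked it at Week 68. That does not follow. Diary collection continues past Visit 14, so an early Visit 14 cuts nothing off. Week 52 is also the re-randomisation point and the baseline for several Period 3 outcomes, which is a likely reason for tying its window to the visit, though the SAP gives none. The Week 52 rule shows that a visit-tied window can be programmed here, and no more.

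A third objection is that a fully visit-tied Week 68, with overlapping days removed from Week 67, only moves the gap. This is correct. For a Day 473 visit the window would be Days 466-472, leaving Week 67 with Days 463-465. That is three entries, so Week 67 would always be missing. Any fix should leave Week 67 alone.

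Finally, the stakes are low. SAP 4.3 lists these Week 68 outcomes as exploratory, SAP 6.2.2.3 allows no inferential test in Periods 3 and 4, and mLOCF results stand beside the observed ones. All of that stands, and it sets the grade rather than removing the point.

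**Conclusion.** The mechanism holds and is minor. The fixed window, the end of diary collection at Visit 18 and the four-day tolerance together leave patients who attend two to four days early with 4 to 6 possible entries against a minimum of 4.

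The excess missing at Week 68 is about 1-4% with clustered visits and 4-10% with an even spread. Both ranges run from reading B at 90% completion to reading A at 80%. They rest on assumed completion rates, independence between days and an assumed distribution of visit days, none of which is in the documents. At 95% completion the excess is smaller still.

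No primary, key secondary or multiplicity-controlled result is touched. Nothing in the documents suggests that early attendance differs by arm, so no directional bias is claimed.

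**What to change.** In SAP 6.2.2.1, keep Days 470-476 as the Week 68 window and add a fallback. When Visit 18 occurs before Day 477 and fewer than 4 entries fall in that window, use the 7 days before the Visit 18 date, with the same 4-entry minimum and the same censoring. Leave the Week 67 window unchanged. If there is no Visit 18, Days 470-476 apply as now.

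Under the same assumptions, the chance of a missing score for a Day 473 visit falls from 27-59% to about 0.3-3.3%, in line with an on-time visit.

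The cost is one sentence and a small change to the programming, with no new data collection. For the few patients who use the fallback, the Week 68 score describes a slightly earlier period and shares days with Week 67: four (Days 466-469) for a Day 473 visit, three for Day 474, two for Day 475 and one for Day 476. A table footnote giving the number of such patients per arm would make this visible.
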